### 6.1.4 Subgroup Analyses

[figure not shown]
Subgroup analyses will be performed on the coprimary endpoints using the FAS. The primary imputation method will be applied for these analyses. The CMH test using the stratification factors from IRT will be the analysis method used. The following subgroups will be considered:

- Geographic region (U.S., Japan, China, Rest of World)
- Country
- Sex (male, female)
- Age group (<65 y, ≥65 y)
- Body weight (<90 kg, ≥90 kg) – from case report form
- Race
- Prior biologic use for psoriasis, psoriatic arthritis and other inflammatory diseases only (yes, no) – from case report form
- Prior systemic treatment use (yes/no)
- Prior phototherapy use (yes/no)
- sPGA (3, 4)
- PASI score (≤20, >20)
- BSA involvement (10-20, >20)
- Duration of disease (< 10 y, ≥ 10 y)
- Age at disease onset (<18, 18-39, ≥40)

Sponsor: Bristol-Myers Squibb  
Protocol no: IM011046

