8.4.7 Suicidal Ideation and Behavior Monitoring	
Subjects who answer yes to Questions 4 or 5 which indicates a suicidal ideation severity level of 4 or 5 or document suicidal behavior or suicidal attempts on the eC-SSRS will have their treatments discontinued and be immediately referred to a mental health professional for further evaluation.
	Clarified to sites to what levels of suicidal ideation Questions 4 and 5 refer.

Protocol Section	Revised Protocol Text	Rationale for Change

Protocol Section	Revised Protocol Text	Rationale for Change
9.2 Populations for Analyses	
Changed to:
 
Full Analysis Set (FAS): All subjects who were randomized to receive assigned study treatment. Following the intent-to-treat principle, subjects will be analyzed according to the treatment group assigned at randomization. The FAS will be the primary efficacy analysis population.
 
Per Protocol Set (PPS): A subset of the FAS who are compliant with study treatment and who do not have any relevant protocol deviations that may impact the coprimary efficacy endpoint assessments (Section 9.6.3). The PPS will be analyzed for the coprimary endpoint comparison according to the treatment assigned at randomization.
 
As-treated Population: All randomized subjects who take at least one dose of study treatment. Subjects will be analyzed according to treatment received. The As-treated population will be for safety analyses.
 	To align populations for testing coprimary efficacy endpoints in order and to clarify that Per Protocol set will be a subset of FAS to assess the sensitivity of coprimary endpoints results based on FAS with respect to data irregularity and deviations
9.4.1.4 Subgroup Analyses for the Coprimary Endpoints	Added: Prior systemic treatment of psoriasis (yes/no)	To determine whether treatment effect sizes of BMS-986165 compared to placebo are similar or how much different with respect to prior use of systemic treatment affects

Protocol Section	Revised Protocol Text	Rationale for Change

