### **4.2 Number of Subjects**

Approximately 600 qualified subjects will be randomized in a 2:1:1 ratio to BMS-986165 6 mg QD, apremilast 30 mg BID, and placebo, respectively. [REDACTED]

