##### **9.4.1.4 Subgroup Analyses for the Coprimary Endpoints**

Subgroup analyses will be conducted for the coprimary efficacy endpoints for the FAS using the analysis described in Section 9.4.1 and the imputation methods described in Section 9.4.1.2. Subgroups to be evaluated will include the following:

- Gender
- Age categories (<65;  $\geq$ 65)
- Race

- Body weight categories (<90 kg;  $\geq$ 90 kg)
- Prior biologic use (yes/no)
- Prior systemic treatment of psoriasis (yes/no)
- Geographic region

In addition, additional subgroups defined for descriptive summaries will be specified in the statistical analysis plan.

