### 6.1 Efficacy Analyses

All efficacy analyses will be performed using the FAS, unless otherwise specified.

Tests of significance of BMS-986165 6 mg QD vs. placebo for the coprimary endpoints will be two-sided with a significance level of 0.05. Both coprimary endpoints need to demonstrate statistical significance to result in a successful study.

The key secondary endpoints will be tested with a two-sided significance level of 0.025 to compare BMS-986165 6mg QD vs. placebo and vs. apremilast. A hierarchical testing approach will be used for testing of

Sponsor: Bristol-Myers Squibb

Protocol no: IM011046

key secondary endpoints (see [Section 6.1.3](#)). Two-sided 95% confidence intervals (CIs) will be provided for all efficacy estimates. [REDACTED]

Coprimary and key secondary efficacy endpoints will be displayed graphically by treatment group and visit, as applicable. All efficacy endpoints will be summarized descriptively.

Due to small sample sizes in China and Japan and differences in stratification factors, analyses will be stratified by a combination of the stratification factors used in randomization. The stratified levels are provided below:

- US/PRIOR USE/< 90 KG
- US/PRIOR USE/≥90 KG
- US/NAÏVE/<90 KG
- US/NAÏVE/≥90 KG
- ROW/PRIOR USE/< 90 KG
- ROW/PRIOR USE/≥90 KG
- ROW/NAÏVE/<90 KG
- ROW/NAÏVE/≥90 KG
- JAPAN/PRIOR USE
- JAPAN/NAÏVE
- CHINA/PRIOR USE
- CHINA/NAÏVE

If there is not at least one subject per treatment group in each of the China and Japan strata, then these regions will be collapsed together to form the following stratified levels for analyses:

- US/PRIOR USE/< 90 KG
- US/PRIOR USE/≥90 KG
- US/NAÏVE/<90 KG
- US/NAÏVE/≥90 KG
- ROW/PRIOR USE/< 90 KG
- ROW/PRIOR USE/≥90 KG
- ROW/NAÏVE/<90 KG
- ROW/NAÏVE/≥90 KG
- ASIA/PRIOR USE
- ASIA/NAÏVE

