## 6.1.1 Primary Endpoints

### 6.1.1.1 Primary Analysis

#### Analysis Model

A stratified Cochran-Mantel-Haenszel (CMH) test will be used to compare the sPGA 0/1 response rates at Week 16 between BMS-986165 6 mg QD and placebo using the stratification factors from IRT specified in [Section 6.1](#). The odds ratio (ratio of odds in BMS-986165 6 mg QD group to the odds in the placebo group) and the corresponding 2-sided 95% CIs and p-values will be reported. Additionally, treatment differences in proportions and the 95% CI for the treatment difference will be provided. The common treatment difference in proportion with the confidence interval, common odds ratio with the confidence interval and p-value will be estimated by the Mantel-Haenszel method consistently.

A similar analysis will be performed to compare the PASI 75 response rates at Week 16 between BMS-986165 6mg QD and placebo.

Sponsor: Bristol-Myers Squibb  
Protocol no: IM011046

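### The subgroup plan tests for an effect within each level but specifies no contrast between levels, although the protocol added prior systemic treatment to learn whether effect sizes differ

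*SAP*

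**What the plan says.** SAP 6.1.4 (Subgroup Analyses) lists 14 factors for the coprimary endpoints in the FAS and names one method: "The CMH test using the stratification factors from IRT will be the analysis method used". Protocol 9.4.1.4 points the same way: "Subgroup analyses will be conducted for the coprimary efficacy endpoints for the FAS using the analysis described in Section 9.4.1", which is the stratified CMH comparison with placebo.

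One factor comes with a stated purpose. Protocol 9.4.1.4 lists "Prior systemic treatment of psoriasis (yes/no)", and the Summary of Changes entry for that section gives the reason for adding it: "To determine whether treatment effect sizes of BMS-986165 compared to placebo are similar or how much different". No such purpose is written for the other factors.

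The plan does not stop at p-values. SAP 6.1 says "Two-sided 95% confidence intervals (CIs) will be provided for all efficacy estimates". The CMH analysis model in SAP 6.1.1.1 reports the odds ratio with its CI, and then: "Additionally, treatment differences in proportions and the 95% CI for the treatment difference will be provided". Both are to be estimated by the Mantel-Haenszel method.

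The visible text of the two documents contains no treatment-by-subgroup contrast, no homogeneity test and no rule for judging consistency across levels.

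**The concern.** A CMH test run inside a subgroup level has the null hypothesis of no treatment effect in that level. The question written for prior systemic treatment is about the difference between two effects. The two can come apart in either direction.

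- When the effect is large and the levels are large, every level is significant whether or not the effects differ.
- When a level is very small, it can miss significance although its effect equals everyone else's.

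So the p-values from the named test carry little information on the stated question. What is at stake is interpretation: whether the report can say, with a pre-specified estimate and interval, how much the effect differs between subjects with and without prior systemic treatment. The coprimary conclusion does not depend on it.

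**Working it through.** The documents state no power or precision for the subgroup analyses, so there is no figure of the plan's own to reproduce.

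**Inputs from the documents**
- Size and allocation, Protocol 4.2: "Approximately 600 qualified subjects will be randomized in a 2:1:1 ratio". This gives 600 × 2/4 = 300 on BMS-986165 and 600 × 1/4 = 150 on placebo.
- Coprimary tests, SAP 6.1: "will be two-sided with a significance level of 0.05".
- Phase 2 PASI 75 at Week 12, Protocol 2.1: 68.9% at 3 mg BID and 6.7% on placebo.

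**Assumptions**
- A two-level factor splits subjects into equal halves, 150 v 75 in each.
- Placebo response is 10% in both halves. BMS-986165 response is 45% in one half and 65% in the other, a true difference of 20 points between the risk differences.
- Tests within a level ignore the IRT strata. Stratifying inside a small level would lower power further.

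**1. Within-level tests.** In the weaker half the pooled rate is (67.5 + 7.5)/225 = 0.333, and the null SE is √(0.333 × 0.667 × (1/150 + 1/75)) = 0.0667. The expected z is 0.35/0.0667 = 5.25. In the other half it is 0.55/0.0706 = 7.8. Both halves are significant in about 100% of simulated trials, so a 20-point difference leaves no trace in the pattern of significance.

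**2. Contrast on the risk-difference scale.**
SE = √(0.45 × 0.55/150 + 0.65 × 0.35/150 + 2 × 0.10 × 0.90/75) = √0.005567 = 0.0746.
z = 0.20/0.0746 = 2.68; power ≈ Φ(2.68 − 1.96) = 76%. Simulation gives about 77%.

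**3. Contrast on the odds-ratio scale.**
Difference in log odds = ln(0.65/0.35) − ln(0.45/0.55) = 0.820.
SE = √(1/(150 × 0.45 × 0.55) + 1/(150 × 0.65 × 0.35) + 2/(75 × 0.10 × 0.90)) = 0.594.
z = 1.38; power ≈ Φ(1.38 − 1.96) = 28%, and simulation agrees. The few expected placebo responders dominate this variance.

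**4. What the planned CIs can show.** At the Phase 2 rates in two equal halves, the 95% half-width for the difference between the two risk differences is 1.96 × √(2 × (0.689 × 0.311/150 + 0.067 × 0.933/75)) = 13 points. A large difference would be visible to a reader who works this out from the level-specific intervals.

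**5. Small levels with an identical effect.** Chance that the small level and the remainder disagree on significance:

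| Small level (active v placebo) | 68.9% v 6.7% | 55% v 10% (assumed) |
|---|---|---|
| 30 v 15 | 0.4% | 11% |
| 10 v 5 | 32% | 67% |

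**6. Homogeneity test with many tiny levels.** Take 12 assumed countries, ten of 10 v 5 and two of 100 v 50, with an identical 55% v 10% effect. A plain Wald chi-square test of equal risk differences rejects in about 26% of trials at nominal 5%. One cause is that a placebo cell of five has no responders with probability 0.9⁵ = 59%, which sets its estimated variance to zero.

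**The case against.** The strongest reply is that the plan already serves an estimation aim. Asking how much effects differ is a request for estimates, and level-specific odds ratios and risk differences with 95% CIs are promised. This stands, and it limits the point. A reader might infer that real differences would go undetected. The documents do not support that, because the intervals allow comparison by eye. What they lack is the contrast itself with its own interval.

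A reader might also infer that the plan will label small subgroups inconsistent or ineffective. Nothing in either document says that a level will be judged on its own p-value; the significance rules in SAP 6.1 cover the coprimary and key secondary endpoints only. Chance disagreement is also confined to very small levels: at 30 v 15 and Phase 2 rates it is 0.4%.

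Three further limits stand. The effect-size aim is written for one factor only, in a change rationale. It is used here as the purpose of the current text, not as a contradiction of it. Power depends heavily on scale (77% against 28%). And a homogeneity test applied to every factor would mislead for country and race.

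Finally, SAP 6.1.3 and 6.1.5 are not visible and material is omitted from 6.1.4, so a contrast in hidden text cannot be excluded.

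**Conclusion.** The point holds as a modest mismatch between a stated question and the named test. For prior systemic treatment the protocol asks about a difference in effect sizes. The visible plan supplies level-specific estimates and CIs, and a test that answers another question. In the worked case the within-level tests show nothing (both significant in about 100% of trials), while a contrast of risk differences would detect the 20-point difference in about 77%.

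These figures rest on equal halves, 10% placebo response, unstratified tests and response rates that are assumptions. A less even split would lower the contrast's power. This is a worthwhile improvement to an exploratory analysis, not a defect in the primary or key secondary analyses.

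**What to change.** In SAP 6.1.4:

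- Keep the planned Mantel-Haenszel risk difference with 95% CI in each level.
- Add one pre-specified exploratory contrast, the difference between the two level-specific risk differences with its 95% CI. Do this at minimum for prior systemic treatment and preferably for the other two-level factors. Name the risk-difference scale in advance.
- For factors with very small levels (country, race, and the China and Japan levels of region), show estimates and CIs only, or pool small levels or use a small-sample method. Do not apply a plain Wald homogeneity test there.
- State that no level is judged effective or ineffective from its own p-value.
- If a contrast already exists in a section not shown here, refer to it from 6.1.4.

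The cost is wording and a few lines of code. The downside is chance findings. If all 14 factors were contrasted on both endpoints, 14 × 2 × 0.05 = 1.4 would be expected below 0.05 with no true differences. Restricted to the ten two-level factors, the figure is 10 × 2 × 0.05 = 1. Hence the exploratory label.

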## 6.2 Safety

Summaries of safety data will be presented by period and treatment group, as applicable, for the As-treated population.

### 6.2.1 Adverse Events

Adverse events will be presented for the number and percentage of subjects and the number of events. Treatment-emergent will be provided in listings. Summary tables will be reported in decreasing frequency based on the BMS-986165 column. Counting for frequency analysis will be by subject and not by AEs, and subjects are only counted once for recurring AEs within each system organ class (SOC) or preferred term (PT); however, the number of total AEs per subject, including multiple occurrences of individual AEs, will also be presented. For summaries of severity, AEs will be reported only at their maximum severity in each subject. Subjects with multiple AEs within a particular SOC or PT will be counted under the category of their most severe event within that SOC or PT.

AE (including deaths) dates will be imputed according to algorithms detailed in [Section 8.0](#). The imputed date of AE onset will be used to assess whether AEs should be considered as treatment-emergent and included in the safety summaries. The original, partial dates will be included in data listings. No imputation will be performed on missing AE seriousness, severity, or relationship; they will be reported as missing.

AEs will be included in a period if the start date of the AE is after the first dispensation date within a period.

An overall summary for the following categories will be presented:

- Deaths
- SAEs
- Related SAEs

Sponsor: Bristol-Myers Squibb

Protocol no: IM011046

- AEs
- Related AEs
- Discontinued treatment due to AEs

The following summaries will also be provided for the following:

- TEAEs by SOC and PT
- Treatment-related TEAEs by SOC and PT
- TEAEs by PT reported in  $\geq 5\%$  of subjects
- TEAEs by PT reported in  $\geq 1\%$  of subjects
- Treatment-related TEAEs by PT reported in  $\geq 5\%$  of subjects
- TEAEs categorized by severity by SOC and PT
- Exposure-adjusted incidence rate (EAIR) for TEAEs by SOC and PT – EAIR is defined in [Section 8.1](#) of the SAP

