## 4.2 Safety

The safety outcomes include the following:

- Adverse events (AEs)
  - Treatment-emergent adverse events (TEAEs) – defined as:
    - AEs which occur after the first dose of study treatment through 30 days after the final dose of the study treatment or subject's participation in the study if the last scheduled visit occurs at a later time.
  - Treatment-emergent adverse events of interest (AEIs) for the following events:
    - Skin-related AEs
    - Infection AEs, including influenza
    - Creatine kinase (CK) elevation (evaluated as lab toxicity grade 2 or higher)
    - Malignancy
  - SAEs
  - Deaths
- Clinical laboratory parameters
  - Absolute and change from baseline values
  - Laboratory abnormalities (as determined by Controlled Terminology Criteria for Adverse Events [CTCAE v5.0] grading) presented as the worst postbaseline toxicity group
  - Shifts from baseline to maximum postbaseline value
  - Potential drug induced liver injury (DILI) is defined as a subject who meets the following criteria:
    - 1) ALT or AST elevation >3 times ULN  
AND  
▪ 2) Total bilirubin >2 times ULN, without initial findings of cholestasis (elevated serum alkaline phosphatase)  
AND  
▪ 3) No other immediately apparent possible causes of liver function test elevation and hyperbilirubinemia, including, but not limited to, viral hepatitis, preexisting chronic or acute liver disease, or the administration of other drug(s) known to be hepatotoxic.
    - ALT or AST elevation >5 times ULN
- Vital signs
  - Absolute and change from baseline values
  - Marked abnormalities defined by the below categories:
    - Heart rate:
      - Value > 100 and change from baseline > 30
      - Value < 55 and change from baseline < -15
    - Systolic blood pressure:
      - Value > 140 and change from baseline > 20

Sponsor: Bristol-Myers Squibb

Protocol no: IM011046

- Value < 90 and change from baseline < -20
- Diastolic blood pressure:
  - Value > 90 and change from baseline > 10
  - Value < 55 and change from baseline < -10
- Electrocardiograms (ECGs)
  - Absolute and change from baseline values
  - Marked abnormalities defined by the below categories:
    - QT interval corrected using Fridericia's formula (QTcF):
      - 450 -< 480 msec
      - 480 -< 500 msec
      - $\geq$  500 msec
      - $30 < \text{change from baseline} \leq 60$  msec
      - Change from baseline > 60 msec
      - Males: < 450 msec,  $\geq$  450 msec
      - Females: < 470 msec,  $\geq$  470 msec

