### 6.3.4 Exposure

#### 6.3.4.1 Duration of Treatment

##### Duration by Group

Overall duration of each treatment, in days, will be calculated for each subject in each treatment group. Subjects are dispensed study treatment at each visit, starting with Day 1 (Week 0) and at each subsequent visit. The date of first dose of study treatment is the Week 0 [redacted] dosing date and is recorded on the eCRF. If this date is missing, then the earliest drug dispensation date will be used. The last dose date is recorded on the end of treatment page in the eCRF. If this date is missing, then the latest date from the [redacted] page or drug accountability return date will be used.

Duration of treatment will be summarized descriptively by randomized treatment group.

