Exposure-adjusted incidence rate (EAIR)	EAIR = $100 * 365.25 * (\text{total number of subjects with the AE}) / \text{total exposure time for the selected AE under each treatment}$ that a subject is exposed. Where total exposure time for each AE within a treatment is calculated as follows: 
 
• If a subject has at least 1 event while on a particular treatment, then the exposure time for that subject and AE on that treatment is: 
 
◦ First AE onset date – treatment start date (of that particular treatment) + 1
 
 
 
• If a subject does not have an event, exposure time for that AE is: 
 
◦ Treatment stop date (of that particular treatment) – Treatment start date (of that particular treatment) + 1 + 30 days (if subject discontinued or subject completed Period 3 and is not rolling into IM011075 study)
 
◦ Treatment stop date (of that particular treatment) – Treatment start date (of that particular treatment) + 1 (if subject completed Period 3 and is rolling into IM011075 study)
 
 
 
• Total exposure time = sum of exposure time for each AE within a treatment
 

First Dose Date – Study	The date a subject received their first dose on Day 1 as recorded in the eCRF Week 0 [redacted] dosing date or the earliest drug dispensation date.

Sponsor: Bristol-Myers Squibb  
Protocol no: IM011046

Last Dose Date – Study	The date of last recorded dose on the eCRF for a randomized subject.
First Dose Date – Period	The date a subject received their first dose as recorded in the eCRF Week 0 █ dosing date or the earliest drug dispensation date for Treatment Period 1 and the earliest drug dispensation date for Treatment Periods 2 and 3.
Last Dose Date – Period	The date of the last visit in the periods – 1. If a subject prematurely discontinues study treatment within a period, the date of last recorded dose on the eCRF will be used as the last dose date for the period.
Percent Change from Baseline	
Percent change from baseline is defined as ([value at post-baseline visit – value at baseline]/value at baseline) x 100.
 
If the baseline value is 0 and the post-baseline value is also 0, then the percent change from baseline is set to 0.
 
If the baseline value is 0 and the post-baseline is >0, then the percent change from baseline value will be missing.

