### 8.3 Missing, Unknown, or Partial Dates

Start Date		Stop Date						
		Complete: yyyymmdd		Partial: yyyyymm		Partial: yyyy		Missing/ Ongoing
<1 st dose	≥1 st dose	<1 st dose yyyymm	≥1 st dose yyyymm	<1 st dose yyyy	≥1 st dose yyyy			
Partial: yyyymm	= 1 st dose yyyymm	2	1	n/a	1	n/a	1	1
	≠ 1 st dose yyyymm		2	2	2	2	2	2
Partial: yyyy	= 1 st dose yyyy	3	1	3	1	n/a	1	1

Sponsor: Bristol-Myers Squibb

Protocol no: IM011046

	≠ 1 st dose yyyy		3		3	3	3	3
Missing		4	1	4	1	4	1	1

1 = Impute as the date of first dose

2 = Impute as the first of the month

3 = Impute as January 1 of the year

4 = Impute as January 1 of the stop year

Note: If the start date imputation leads to a start date that is after the stop date, then there is a data error and the start date is not imputed.

Imputation rules for partial or missing stop dates:

1. Initial imputation
  - a. For partial stop date "mmyyyy", impute the last of the month.
  - b. For partial stop date "yyyy", impute December 31 of the year.
  - c. For completely missing stop date, do not impute.
2. If the stop date imputation leads to a stop date that is after the death date, then impute the stop date as the death date.
3. If the stop date imputation leads to a stop date that is before the start date, then there is a data error and the stop date is not imputed.

Imputation rules for partial or missing death dates:

1. If death year and month are available but day is missing:
  - a. If "mmyyyy" for last contact date = "mmyyyy" for death date, set death date to the day after the last contact date.
  - b. If "mmyyyy" for last contact date < "mmyyyy" for death date, set death date to the first day of the death month.
  - c. If "mmyyyy" for last contact date > "mmyyyy" for death date, data error and do not impute.

If both month and day are missing for death date or a death date is totally missing, set death date to the day after the last contact date.

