## 8.4 Study Periods

Period 1 = Week 0 to Week 16 visit date

Period 2 = Week 16 visit date +1 to Week 24 visit date

Period 3 = Week 24 visit date +1 to Week 52 visit date

Follow-up = 4 week follow-up period

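### The AE period rule in SAP 6.2.1 leaves post-dose Day 1 AEs, and AEs with onset imputed to first dose, in no period, although SAP 8.4 starts Period 1 at Week 0

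*SAP*

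**What the plan says.** SAP 6.2 presents safety by period and treatment group. SAP 6.2.1 gives the allocation rule for adverse events: "AEs will be included in a period if the start date of the AE is after the first dispensation date within a period". The preceding paragraph of 6.2.1 says what partial onset dates are for: "The imputed date of AE onset will be used to assess whether AEs should be considered as treatment-emergent and included in the safety summaries".

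Four other places in the SAP bear on the rule:

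- **8.4 Study Periods:** "Period 1 = Week 0 to Week 16 visit date". Periods 2 and 3 start one day after the Week 16 and Week 24 visits.
- **8.3 Missing, Unknown, or Partial Dates:** the first imputation code for start dates is "1 = Impute as the date of first dose".
- **6.3.4.1 and 8.1:** dispensing begins on Day 1 ("Subjects are dispensed study treatment at each visit, starting with Day 1 (Week 0"), and the study first-dose date is "The date a subject received their first dose on Day 1 as recorded in the eCRF Week 0", with the earliest dispensation date as the alternative.
- **4.2 Safety:** treatment-emergent events are "AEs which occur after the first dose of study treatment through 30 days after the final dose of the study treatment", or to a later last scheduled visit.

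**The concern.** In Period 1 the rule sets a strict inequality against Day 1. An event that begins a few hours after the first tablet has an onset date equal to the dispensation date, fails the test, and has no earlier treatment period to fall into. By SAP 4.2 it is treatment-emergent, and by SAP 8.4 it lies in Period 1.

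The imputation makes this more than a matter of early reactions. Setting an unknown onset to the first-dose date is a device for counting the event when it may have begun on treatment. The period rule then rejects exactly that date, so neighbouring paragraphs of 6.2.1 work against each other.

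Period 1 is the only placebo-controlled part of the trial, because placebo subjects switch at Week 16. Its AE tables are the main randomized safety comparison with placebo. A programmer who follows 6.2.1 and one who follows 8.4 would get different counts from the same data.

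**Working it through.** The plan gives no figure to reproduce; this is a check of date rules.

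**Inputs.** Target days from SAP 8.5: Week 16 = Day 113, Week 24 = Day 169, Week 52 = Day 365. First dispensation and first dose = Day 1 (SAP 6.3.4.1, 8.1). Dispensing that opens Periods 2 and 3 is taken as Day 113 and Day 169. Section 6.2.1 has no upper limit, so the period ends come from 8.4.

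**Rules compared.**

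- 6.2.1: onset day > dispensation day, with the 8.4 period end as upper limit.
- 8.4: Period 1 = Days 1–113, Period 2 = Days 114–169, Period 3 = Days 170–365.

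| Onset day | Period by 6.2.1 | Period by 8.4 |
|---|---|---|
| 1, after dosing | none (1 > 1 is false) | 1 |
| 1, imputed to first dose | none (1 > 1 is false) | 1 |
| 2 | 1 | 1 |
| 113 | 1 | 1 |
| 114 | 2 | 2 |
| 169 | 2 | 2 |
| 170 | 3 | 3 |

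Of the days tested, the rules differ only on Day 1. For Periods 2 and 3 the strict inequality matches the plus-one starts in 8.4.

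**Illustration with a partial date.** Suppose dispensation and first dose are both on 3 May, and an ongoing event has its onset recorded only as May of that year. The 8.3 table gives code 1, so the onset becomes 3 May. By 6.2.1, 3 May is not later than 3 May: no period. By 8.4, 3 May is Week 0: Period 1.

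**Reach of the imputation.** Code 1 appears in three start-date rows of the 8.3 table: partial date in the first-dose month, partial date in the first-dose year, and fully missing. In each row it fills the four columns where the stop date is on or after first dose (complete, year and month, year only) or is missing or ongoing. That is 3 × 4 = 12 cells. Every onset imputed through them fails the Period 1 test when dispensing and first dose share a date.

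**Cross-check with the exposure-adjusted rate.** SAP 8.1 sets exposure for a subject with an event to "First AE onset date – treatment start date (of that particular treatment) + 1". For a Day 1 onset this is 1 − 1 + 1 = 1 day. The rate calculation therefore admits Day 1 onsets, and the same event could appear in the EAIR table and be absent from the Week 0–16 table.

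**Candidate corrections.** If every period used on-or-after, Day 113 would fall in Periods 1 and 2, and Day 169 in Periods 2 and 3. If only Period 1 used it, every tested day would match 8.4.

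**The case against.** The strongest reply is that 6.2.1 says *if*, not *only if*. On that reading 8.4 sets the period limits, 6.2.1 is a loosely worded allocation sentence, and the imputation rule and the EAIR formula show that the SAP means Day 1 events to count. The evident intent is a fair point, but it supports the correction. The SAP nowhere tells the programmer to fall back on 8.4 when 6.2.1 does not admit an event.

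A second point is that the agreement for Periods 2 and 3 needs some help from the reader. Under 8.4 the Week 16 visit date belongs to Period 1, so the first dispensation strictly within Period 2 would be Week 20. The visit windows in 8.5, which use the Week 16 and Week 24 dispense dates as boundaries, support the sensible reading. The corrected text should name those visits.

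Third, SAP 8.5 places Day 1 in Baseline and starts the Period 1 windows on Day 2. Those windows assign assessments to analysis visits and do not govern AE onset. Fourth, a separate data presentation plan may resolve same-day events. It is not available here, and it would not remove the inconsistency in the SAP.

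What stands on size: the number of affected events is unknown and may be small, the 12 cells are not a frequency, and the rule is the same in every arm, so no difference between arms is claimed.

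**Conclusion.** The concern holds. Followed as written, SAP 6.2.1 omits from the Week 0–16 AE tables the events that start on Day 1 after the first dose and those whose onset was imputed to the first-dose date, contrary to SAP 8.4.

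The omission can only reduce counts. Event counts fall by one for each such AE. Subject counts fall only where the subject has no other Period 1 event in the same system organ class or preferred term, because subjects are counted once.

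The conclusion assumes that first dispensation and first dose share a date. The SAP places both on Day 1, and they coincide by construction when the dosing date is missing and dispensation is substituted. A subject whose recorded first dose is later than dispensation is not affected. Day 1 events known to precede dosing, such as SAEs collected from consent under Protocol 8.2.2, are properly left out.

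Efficacy, the EAIR formula, listings, and the laboratory, vital sign and ECG summaries are not governed by this rule. The point should be corrected, but it does not threaten the primary conclusion.

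**What to change.** In SAP 6.2.1, state that Period 1 includes AEs with an actual or imputed onset on or after the date of first dose, except those known to have started before dosing. For Periods 2 and 3 keep the strict inequality, and name the Week 16 and Week 24 dispensation dates so that the rule agrees with 8.4. Put the same same-date convention in the TEAE definition in 4.2.

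The cost is one sentence and one matching clause. The one downside is that a Day 1 event whose timing relative to the first dose is unknown would be counted as treatment-emergent, which is the cautious direction for safety.
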